## INVESTIGATIONAL PLAN (brief overview)

### Study Design

The study design is a between-subjects randomized controlled trial. Qualtrics will randomly assign participants to one of four study arms in the Qualtrics survey. Participants will have an equal chance of being randomized to any of the trial arms.

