Following online consent, Qualtrics will equally randomize participants to one of the four front-of-package label conditions: nutrient warning, Nutri-Score, GDA, or a no-label condition. On Qualtrics, participants will complete three tasks. They will be asked to complete a selection task, in which participants will be asked to select which fruit drink is higher in sugar, which they would rather buy, and which is most unhealthy. The fruit drinks will be displayed with the labels corresponding to the participant's randomly assigned label condition. We will only include selection tasks for one type of product due to survey space constraints. Following the selection tasks, the participant will be asked to complete a single product assessment task. They will view a prompt that reads: "The next questions are about food products. You will look at a few different products and answer questions about each one. Please keep in mind that this study seeks to evaluate your survey responses and not the sale of the product." Then, they will answer a series of questions about the yogurt, cookies, and sliced bread, which will show the participant's randomly assigned label condition. The participants will answer all questions about one product at a time (displayed in random order). After these, the participants will answer objective understanding and PME questions about the breakfast cereal. The breakfast cereal is always displayed last as the nutrient warning condition contains two labels. Finally, the participants will be randomly assigned to see the yogurt, cookies, or sliced bread again (one product only). However, this time, the product will not fashion a label. Instead, the three label types (nutrient warnings, GDA, and Nutri-Score) will be displayed underneath the product and the participant will be asked to select the most discouraging label. The study will end with standard demographic questions.

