### *Secondary Outcomes*

We hypothesize that the nutrient warning label (compared to other label types) will:

1. Have higher perceived message effectiveness.
2. Be the most discouraging label.

We hypothesize that the nutrient warning label (compared to all other conditions) – and all conditions compared to the control – will:

1. Increase the ability to correctly identify the most unhealthy product when compared with two options.
2. Increase the ability to correctly identify whether a single product contains excess sugar, saturated fat, or sodium.
3. Lower intentions of purchasing a product high in the nutrient of concern in the next week if it were available.

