### **Statistical Methods**

We will use complete case analysis to handle any missing data. We will descriptively report unadjusted means (and standard deviations) and percentages for the primary and secondary outcomes.

We will use a two-sided critical alpha of 0.05 to conduct all statistical tests.

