### **Sensitivity Analyses**

For PME, we will take the average of the 3 items for each product type if  $\alpha > .70$ . For all outcomes assessed between-subjects only, we will then assess whether the outcomes vary by study arm with regression models (linear for continuous outcomes and logistic for dichotomous outcomes).

For outcomes with multiple measurements per-person, we will fit mixed effects linear regression models for continuous outcomes (including PME) and a mixed effects logistic regression model for binary outcomes (including product selection, label selection, identification of healthier products), treating the intercept as random to account for repeated measures.

We will include indicator variables for warning message (between-subjects) and product type (within-subjects), as well as an interaction of warning message and product type. We will use postestimation commands to conduct pairwise comparisons of the predicted means to examine differences by all label types. We will correct for multiple comparisons. To evaluate the most discouraging label, we examine the proportion of participants that selected each warning label as the most discouraging and will conduct z-

tests to explore statistical significance of these differences. To assess whether the effect of the warning label on the primary outcomes differs by education, we will test for an interaction of warning label with low versus high education level (specified as dummy variables) and use a Wald chunk test to determine the joint interaction. We will use postestimation commands to predict means by warning label and education level and conduct pairwise comparisons of the predicted means.

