### Sample Size and Power

Using an ANOVA model in G.Power. 3.1.9.4, we estimate that with a sample of ~8,000, alpha of 0.05, and 80% power, we can detect an effect of  $f=0.037$  for each of the primary outcomes between each arm and the control, which translates to an odds ratio of 1.14.

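### The choice of most discouraging label follows exposure to one assigned label in three of four arms, but its analysis has no split by arm to show whether that exposure matters

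*Combined protocol and SAP*

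**What the plan says.** Study Steps fixes the order. Participants see the assigned label (none in control) on the fruit drinks, then on yogurt, cookies and sliced bread, then on the cereal. Only afterwards, for one of the three middle products shown again without its label, "the three label types (nutrient warnings, GDA, and Nutri-Score) will be displayed underneath the product and the participant will be asked to select" the one that discourages most. Each person makes one choice among three options. The measurement table randomises the display of the options.

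The hypothesis, under Secondary Outcomes in the SAP, is that the nutrient warning will "Be the most discouraging label".

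The section headed Sensitivity Analyses contains two statements on this outcome:

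- The specific one is "To evaluate the most discouraging label, we examine the proportion of participants that selected each warning label as the most discouraging", followed by z-tests of the differences. It names no arm, no split by arm and no carry-over check.
- Earlier in the section, label selection is listed among the binary outcomes for a mixed-effects logistic model with a random intercept and indicators for the between-subjects message. That model is introduced for outcomes measured several times per person.

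**The concern.** Before the choice, a label-arm participant has met one of the three options repeatedly and rated it. One perceived-message-effectiveness item asks how far the label discourages consumption, in almost the same terms as the final question. Study Steps names these items explicitly for the cereal. The SAP averages them for each product type, which suggests that they are asked for other products too. The other two labels have not yet been shown to that participant in the study.

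Exposure and rating could raise the choice of one's own label through familiarity or consistency, or lower it through habituation. If the effect differs between a text warning, a colour grade and a numeric panel, the pooled shares mix preference with the effect of the preceding survey. A stated directional hypothesis, in a study meant to inform a labelling law, would then rest partly on task order. Randomisation lets the trial examine this directly, but the governing sentence does not use it.

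**Working it through.** **Inputs from the documents.** Sample size and error rates: "a sample of ~8,000, alpha of 0.05, and 80% power". Sidedness: "We will use a two-sided critical alpha of 0.05 to conduct all statistical tests". Allocation: "Participants will have an equal chance of being randomized to any of the trial arms", so about 2,000 per arm. The documents give no expected choice shares and no carry-over size, so both are assumed below.

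**The plan's own figure.** The stated f = 0.037 reproduces as a four-group one-way ANOVA. Noncentrality is 8,000 × 0.037² = 10.95 on 3 and 7,996 df, giving power of 80.2%. The odds ratio is exp(2 × 0.037 × π/√3) = 1.14, as stated. This figure concerns the primary outcomes; the label choice has none of its own.

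**Effect of pooling.** Let c be the shift towards one's own label in a label arm, taken equally from the other two labels. With four equal arms:

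- pooled warning share = p_W + (c_W − c_G/2 − c_N/2)/4
- pooled GDA share = p_G + (c_G − c_W/2 − c_N/2)/4
- bias in the warning-minus-GDA difference = 1.5(c_W − c_G)/4 = 0.375(c_W − c_G)

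Equal shifts therefore give zero bias. Only the difference between the shifts matters.

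**Illustrations.** Each person picks one label, so the variance of the difference d is (p_W + p_G − d²)/N, with N = 8,000.

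| True shares W/G/N | Assumed shift | Pooled W | Pooled G | Difference (points) | z |
|---|---|---|---|---|---|
| 1/3 each | +10 or −10 in every label arm | 0.3333 | 0.3333 | 0 | 0 |
| 1/3 each | +5, warning arm only | 0.3458 | 0.3271 | 1.9 | 2.04 |
| 1/3 each | +10, warning arm only | 0.3583 | 0.3208 | 3.75 | 4.07 |
| 1/3 each | −10, warning arm only | 0.3083 | 0.3458 | −3.75 | −4.15 |
| 50/25/25 | +10, warning arm only | 0.5250 | 0.2375 | 28.75 (true 25) | 31.2 |
| 50/25/25 | −10, warning arm only | 0.4750 | 0.2625 | 21.25 (true 25) | 22.8 |

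At an unadjusted 0.05 level, with a true tie, the 5-point case gives a significant pooled difference about 53% of the time and the 10-point case about 98%. With shares of 50/25/25, the order of warning and GDA would reverse only if the two shifts differed by more than 0.25/0.375 = 67 points.

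**What a split by arm can show at the planned size.**

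- A 4 × 3 chi-square test (6 df) has 80% power at noncentrality 13.62, so w = √(13.62/8,000) = 0.041. The 5-point case above has w = 0.0455 (noncentrality 8,000 × 0.0455² ≈ 16.6), so the test would have more than 80% power.
- One label arm against control (2,000 against 2,000) detects an own-label shift of 4.2 to 4.4 points with 80% power, for base shares of 1/3 to 1/2.
- Control arm alone, near equal shares: the 95% half-width for a between-label difference is 1.96 × √((2/3)/2,000) = 3.6 points, against 1.8 for N = 8,000. The 80%-power detectable difference is 2.80 × √((2/3)/2,000) = 5.1 points, against 2.6.

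**The case against.** The plan is not silent on arm. It lists label selection under a model with arm indicators, and it says that between-subjects outcomes will be compared across arms by regression. That much stands: the fault is an unreconciled specification, not a clear decision to ignore arm. But the mixed model is for repeated measures, and the linear and logistic models offered do not directly suit one three-way choice. Neither statement says which estimate answers the hypothesis.

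The tied-share example is the most sensitive case available. With a clear true gap, plausible carry-over does not change the ranking. The SAP also promises a correction for multiple comparisons just before the z-test sentence. If that covers the three pairwise tests, the Bonferroni critical value is 2.39, and the 5-point case would be significant only about 36% of the time. Both points stand and limit the size of the concern. Randomised product and option order are sensible, but they deal with product and position, not prior exposure.

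A reader might infer that the control-arm estimate should replace the pooled one as the main result. The documents do not compel that. It sets aside three quarters of the sample to address an effect that has not been shown. A true 4-point difference near equal shares would have about 59% power in control alone, against about 99% pooled.

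**Conclusion.** The point holds in a limited form. The task order, the single-label exposure and rating in three of the four arms, and the absence of an arm term in the governing sentence are all on the page. So is the mismatch between that sentence and the repeated-measures listing.

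A reader might go further and infer that carry-over does enter the answer. The documents do not support this: they give no evidence of carry-over, of its direction, or of a difference between labels, and equal carry-over cancels exactly under the planned allocation. The conditional statement is the defensible one. If own-label shifts differ, the pooled warning-minus-GDA difference is biased by 0.375 times the difference in shifts (1.9 points for 5, 3.75 for 10). This assumes that each shift is drawn equally from the other two labels. It could decide the conclusion when shares are close, and it would not when they are far apart. Pooled shares alone cannot show how much of a difference reflects exposure.

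This is one secondary outcome. Both primary outcomes are collected before the choice task and are unaffected. It is a low-cost improvement, not a flaw in the trial's main result.

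**What to change.** In the Sensitivity Analyses section of the SAP:

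1. Keep the pooled proportions and their tests.
2. Add the choice proportions by assigned arm, with a 4 (arm) × 3 (label) chi-square test for carry-over. A significant result shows that exposure matters, not that the pooled comparison is biased, because equal carry-over would also trigger it. Read it with the shares by arm.
3. Prespecify the control-arm proportions (about 2,000 participants, no earlier study label) as a sensitivity analysis.
4. State that the conclusion on the most discouraging label will be qualified if the control-arm ranking differs from the pooled one.
5. Reconcile the wording: remove label selection from the repeated-measures binary outcomes, or name a model suited to one three-way choice per person.

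The planned survey already yields the data needed, with no change to the tasks or sample size. The cost is SAP text, one additional test, and a control-arm estimate with half the precision of the pooled one. Close rankings in that arm should therefore be read with their intervals.

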### Sample Size and Power

Using an ANOVA model in G.Power. 3.1.9.4, we estimate that with a sample of ~8,000, alpha of 0.05, and 80% power, we can detect an effect of  $f=0.037$  for each of the primary outcomes between each arm and the control, which translates to an odds ratio of 1.14.

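### The 80% power claimed for OR 1.14 in each arm-versus-control comparison belongs to the four-arm omnibus test; pairwise power at that OR is about 54% at best

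*Combined protocol and SAP*

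**What the plan says.** The power statement in the Sample Size and Power section reads "Using an ANOVA model in G.Power. 3.1.9.4, we estimate that with a sample of ~8,000, alpha of 0.05, and 80% power", and reports a detectable effect of f = 0.037 "for each of the primary outcomes between each arm and the control, which translates to an odds ratio of 1.14". It gives neither the number of groups used in the ANOVA nor a reference rate for either binary primary outcome.

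The Study Design section sets out four arms and states "Participants will have an equal chance of being randomized to any of the trial arms", so about 2,000 people per arm. The primary hypotheses compare the nutrient warning with GDA, with Nutri-Score and with the no-label control. The Statistical Methods section says "We will use a two-sided critical alpha of 0.05 to conduct all statistical tests". The Sensitivity Analyses section plans pairwise comparisons across all label types and adds "We will correct for multiple comparisons", without naming the method or the family. No other power calculation is given.

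**The concern.** An omnibus ANOVA asks whether any of the four arms differ, and it uses the whole sample. A comparison of one arm with control asks a narrower question and uses half the sample. The sentence attaches a single detectable effect to each arm-versus-control comparison, yet the size of f suggests that it came from the omnibus test. The translation to an odds ratio, the treatment of binary outcomes as continuous, and the uncorrected alpha also looked unsafe.

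This is the plan's only statement of sensitivity, and it covers both primary outcomes in a study meant to inform national labelling policy. If nutrient warning versus GDA or Nutri-Score came out non-significant, a reader relying on this paragraph would believe that an effect of OR 1.14 had an 80% chance of being detected, and could wrongly treat it as largely excluded.

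**Working it through.** **Inputs from the documents.** N about 8,000, alpha 0.05, power 80%, f = 0.037 and OR 1.14 (Sample Size and Power); four equal arms (Study Design); two-sided tests (Statistical Methods). Each primary outcome is one two-option choice about fruit drinks, so there are no repeated measures to add information. **Assumption:** the reference rate, which the documents do not give; 10% to 50% is shown.

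**1. Reproducing f = 0.037.** For a one-way ANOVA the noncentrality is λ = N·f².

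- Four groups, N = 8,000: λ = 8,000 × 0.037² = 10.95 on 3 and 7,996 df. Power is 80.2% and the minimum f for 80% power is 0.0369. This matches the plan.
- Two groups, N = 4,000 (the real arm-versus-control comparison): λ = 4,000 × 0.037² = 5.48 on 1 and 3,998 df. Power is 64.8% and the minimum f is 0.0443.
- Two groups, N = 8,000: the minimum f is 0.0313.

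None of the other combinations tried (two, three or four groups, N of 4,000 or 8,000, several alphas) gives 0.037 at 80% power. The nearest is two groups sharing all 8,000 at alpha 0.05/3, with f = 0.0362, and that would need 4,000 per arm.

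**2. Reproducing OR 1.14.** d = 2f = 0.074, and exp(0.074 × π/√3) = 1.144. The step d = 2f is the two-group identity. With four groups it holds only if the arms split two against two. For an omnibus f of 0.037 the largest pairwise d is:

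- two arms against two: 2f = 0.074;
- one arm against three equal arms: 4f/√3 = 0.085;
- two extreme arms, the other two midway: f√8 = 0.105.

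So a four-group f does not translate to one pairwise odds ratio.

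**3. Pairwise power at OR 1.14, binary outcome.** With a 50% reference rate the comparison rate is 1.14/2.14 = 0.5327, a difference of 0.0327. SE = √[(0.5 × 0.5 + 0.5327 × 0.4673)/2,000] = 0.01579, so z = 0.0327/0.01579 = 2.071.

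- Two-sided 0.05: Φ(2.071 − 1.960) = 54.4%.
- Bonferroni, three contrasts: Φ(2.071 − 2.394) = 37.3%.
- Bonferroni, six contrasts: Φ(2.071 − 2.638) = 28.5%.

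The maximum over all reference rates is also 54.4%.

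**4. Other rates, and the OR that 80% power does deliver (2,000 per arm).** The first figure in each cell is for an increase over the reference rate, the second for a decrease (OR shown as its reciprocal). Rates above 50% mirror those below.

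| Reference rate | Power at OR 1.14, alpha 0.05 | Detectable OR, alpha 0.05 | Detectable OR, 0.05/3 | Detectable OR, 0.05/6 |
|---|---|---|---|---|
| 50% | 54.4% | 1.194 | 1.228 | 1.247 |
| 30% | 48.5% / 46.5% | 1.209 / 1.218 | 1.245 / 1.257 | 1.265 / 1.280 |
| 20% | 39.3% / 36.8% | 1.240 / 1.258 | 1.280 / 1.306 | 1.304 / 1.334 |
| 10% | 24.7% / 22.7% | 1.323 / 1.371 | 1.378 / 1.446 | 1.410 / 1.491 |

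In percentage points at a 50% rate: 1.194/2.194 = 54.4%, a difference of 4.4 points; 1.228/2.228 = 55.1%, 5.1 points; 1.247/2.247 = 55.5%, 5.5 points.

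**5. Sample size that OR 1.14 would need pairwise.** n = (1.960 + 0.842)² × 0.4989/0.0327² ≈ 3,660 per arm (3,663 with pooled variance), or about 14,650 in four arms, before any multiplicity correction.

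**The case against.** The best reply has four parts.

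- **The 54% depends on the scale.** It uses the rounded OR on a two-proportion test. The unrounded 1.144 gives 56.4%, and reading f = 0.037 as a two-group standardised difference of 0.074 gives 64.8%. This is correct: the 54% reflects both the omnibus mislabel and the conversion to an odds ratio. All three figures are still well below 80%.
- **The hypothesised pattern is kinder.** If the nutrient warning differs from three equal arms, omnibus f = 0.037 implies d = 0.085 and about 77% uncorrected power for each warning contrast. This is also correct, but d = 0.085 converts to OR 1.17 by the plan's own route. That is a larger effect than the one stated, and the power is still short of 80% before correction.
- **Nothing in the design turns on OR 1.14.** The plan does not call it a target or a smallest important effect, and it plans no equivalence or futility inference. That stands: over-reading a null result is a risk for readers, not a planned analysis. The sentence is nevertheless a factual claim about the primary comparisons.
- **The correction is unspecified.** The Bonferroni figures for three and six contrasts are illustrations, because the plan names neither method nor family. That stands too, but the conclusion holds without any correction.

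**Conclusion.** The statement is wrong as written. Both stated numbers reproduce, but f = 0.037 is the four-arm omnibus figure, and the OR of 1.14 comes from applying a two-group conversion to it. For the pairwise contrasts in the primary hypotheses, power at OR 1.14 is at most 54%, and about 37% or 28.5% at a 50% rate under Bonferroni for three or six contrasts. The OR detectable with 80% power is about 1.19 at best, and 1.24 to 1.26 at a 20% rate, uncorrected.

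These figures rest on assumed reference rates and a full 2,000 evaluable people per arm. The planned exclusions and complete-case analysis would reduce that number and lower power further. The error does not show that the trial is too small: at reference rates between 20% and 80%, odds ratios from about 1.19 to 1.26 are detectable pairwise without correction.

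**What to change.** Keep N at about 8,000 and rewrite the paragraph:

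- Label f = 0.037 as the detectable effect of the four-group omnibus test, and drop its translation to an arm-versus-control OR.
- State the pairwise detectable effect from a two-proportion calculation on the expected evaluable number per arm. Suitable wording, if 2,000 per arm are evaluable: *With about 2,000 per arm, 80% power and two-sided alpha 0.05, each pairwise comparison can detect an OR of 1.19 (4.4 percentage points) at a 50% reference rate and 1.24 to 1.26 at a 20% rate. After Bonferroni correction for the three nutrient-warning contrasts, these become 1.23 (5.1 points) and 1.28 to 1.31.*
- Say that the reference rates are assumptions. Name the multiplicity method and the family of contrasts, so that the power statement and the planned analysis use the same alpha.

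The cost is one paragraph of SAP text and a somewhat less favourable stated sensitivity. No participants are added and the design does not change.

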### Outliers and Exclusions

We will exclude participants from analysis if they are duplicate responders, complete the study in less than two minutes, or if they do not answer at least one primary or secondary outcome.

## SAFETY MANAGEMENT

Provided that this study is conducted completely online, and participants do not have any interactions with study staff there is no anticipation of adverse events. However, the investigators have provided an email to contact as well as the IRB contact information, on the consent form, should a participant be concerned about any aspects of the research study.

## DATA COLLECTION AND MANAGEMENT

Researchers will store the study data on a remote terminal server, and only research investigators and staff will have access to the data.

## RECRUITMENT STRATEGY

Participants will be Offerwise participants who have voluntarily signed up to complete tasks remotely, including research surveys. Our study sample will include only those who self-enroll in the study based on interest, availability, and meeting the inclusion criteria. There is no specific advertisement for this study. Rather, Offerwise identifies users for the survey based on the inclusion criteria (age 18 or older and resides in Colombia) and informs them of the study opportunity.

